5.1.1.6 Hepatotoxicity

Evidence of hepatobiliary injury was observed in animals administered relatively high doses of GDC-0853 in repeat-dose toxicity studies. Dose-dependent increases in ALT, AST, and/or bilirubin have been observed in rats administered ≥ 6 mg/kg/day ($\geq 17 \mu\text{M}\cdot\text{h}$) and dogs administered ≥ 10 mg/kg/day ($\geq 36 \mu\text{M}\cdot\text{h}$), with corresponding microscopic changes in the liver of dogs administered 25 mg/kg/day ($180 \mu\text{M}\cdot\text{h}$). The hepatotoxicity findings in dogs were associated with moribundity in two high-dose animals. The NOAEL for these findings was considered to be 10 mg/kg ($36 \mu\text{M}\cdot\text{h}$) in dogs, the most sensitive species, given the absence of GDC-0853-related hepatotoxicity at this dose when administered for 9 months. These findings were fully reversible and considered monitorable by changes in plasma transaminases and bilirubin that occurred at doses lower than those producing histopathology findings (see the GDC-0853 Investigator's Brochure for further details).

In clinical studies to date, including single dosing and multiple dosing for 14 days in healthy subjects and QD dosing for over 1 year in patients with hematological malignancies, there have been no adverse events of liver enzyme elevations or trends toward elevations in laboratory evaluations.

As a safety risk-mitigation measure, to be eligible for the study, AST and/or ALT levels should be no more than $1.5 \times \text{ULN}$, and total bilirubin levels should be normal at screening. Safety monitoring for potential hepatotoxicity includes baseline and routine evaluations of AST/ALT and total bilirubin levels throughout the study as outlined in the schedule of assessments. The local prescribing information for MTX should also be consulted.

Laboratory results of Grade ≥ 3 ($> 5 \times \text{ULN}$) AST or ALT elevation are adverse events of special interest and should be reported to the Sponsor in an expedited manner as outlined in Section 5.2.3.

Guidelines for the management of study treatment in the event of hepatotoxicity in patients are provided in Table 5. Please refer to the GDC-0853 Investigator's Brochure for further details.

5.1.1.7 Cardiovascular Effects

GDC-0853 is considered to have a low potential to cause QT interval prolongation or to directly affect other CV parameters, at therapeutic exposures. A minimal increase in QTc (7 ms or 3%) interval was noted at 45 mg/kg in the single-dose CV safety pharmacology study in telemetry-instrumented dogs. Based on extrapolated/interpolated toxicokinetic data, the unbound C_{max} at 45 mg/kg (considered a NOAEL) and no-observed-effect level of 15 mg/kg were [REDACTED]

[REDACTED] There have been no GDC-0853-related changes in ECG parameters in the 4-week or 9-month dog toxicity studies.

Analysis of ECG data from the SAD and MAD studies in healthy subjects did not demonstrate any significant increase in either QRS interval or QTcF intervals. However, cardiac safety will be evaluated in all patients at baseline and throughout the study, with routine monitoring of vital signs (including heart rate and blood pressure), collection of triplicate ECGs with PK-matched timepoints, routine safety ECGs, and collection of adverse events (see Appendix 1 and Appendix 2).

Management of patients with sustained QTcF prolongation (QTcF that is > 500 ms and/or > 60 ms longer than the baseline value on at least two ECG measurements > 30 minutes apart) should include close monitoring, with ECGs repeated at least hourly until two successive ECGs show resolution of the findings, correction of any electrolyte abnormalities, and possible discontinuation of other concomitant medications that are known to prolong the QT interval. Consultation with a cardiologist or electrophysiologist is recommended, to help in the management of such patients. The Medical Monitor should be notified as soon as possible.

Guidelines for management of study treatment in the event in the event of CV effects in patients are provided in Table 5.

Please refer to the GDC-0853 Investigator's Brochure for further details.

5.1.1.8 Vascular Inflammation

Vascular inflammation (vasculitis) was observed in dogs administered GDC-0853 at ≥ 10 mg/kg/day (≥ 56 $\mu\text{M}\cdot\text{h}$) in the 4-week toxicity study, and these changes were not completely reversed by the end of the 4-week recovery period. There was no consistent correlation with any clinical biomarkers. However, in the 9-month toxicity study in dogs, no GDC-0853-related vascular inflammation was observed up to the highest dose of 10 mg/kg/day (36 $\mu\text{M}\cdot\text{h}$), which is considered to be the NOAEL (AUC) for the canine vascular inflammation findings. [REDACTED]

[REDACTED] The translatability of these findings to humans is unknown; however, Beagle dogs are susceptible to spontaneous development of polyarteritis syndrome (Snyder et al. 1995) and may be more sensitive to any drug-induced effects. Further, there are several examples of approved therapies for which there is no correlation between the finding of vasculitis in dogs or rats at clinically relevant exposures and adverse outcomes in patients (FDA 2011).

As a safety risk-mitigation measure, patients with a history of vasculitis, including RA associated vasculitis, will be excluded from the study, and CBC, creatinine, and urinalysis will be monitored in all patients during the study. Study drug should be discontinued in any patient who develops an adverse event of vasculitis, and the patient should enter safety follow up.

Guidelines for management of study treatment in the event of vasculitis in patients are provided in Table 5.

Please refer to the GDC-0853 Investigator's Brochure for further details.

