The risk to human safety based on toxicological findings of vascular inflammation in animal studies is uncertain. As a safety risk-mitigation measure, patients with a history of vasculitis, including RA-associated vasculitis, will be excluded from the study, and complete blood counts (CBC), creatinine levels, and urinalysis findings will be monitored in all patients during the study. Study drug should be discontinued in any patient who develops an adverse event of vasculitis, and the patient should enter the safety follow-up period.

Overall, GDC-0853 has been well tolerated in Phase I healthy subjects and oncology studies. On the basis of the compelling mechanism for BTK inhibition in RA, the risk-benefit ratio for this study is deemed acceptable. The safety profile of GDC-0853 will be further characterized in this Phase II study, and a robust safety monitoring plan that describes the potential risks for GDC-0853 and the risk-mitigation strategies to minimize risks for the patients in this trial is provided in Section 5.1.

Please refer to the most recent GDC-0853 Investigator's Brochure for additional details on clinical and nonclinical studies and additional safety information.

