4.6.2 Study Treatment Discontinuation

Patients must *permanently* discontinue study treatment with both oral study drug and SC comparator drug (*however patients should be asked to remain in the blinded study through Week 12 even if their study treatment is discontinued in order to minimize missing data that limits study interpretability*) if they experience any of the following:

- *Pregnancy (the patient may still remain in the blinded study at the investigator's discretion)*
- Anaphylaxis or other severe hypersensitivity reaction
- Malignancy
- Any serious infection or infection requiring treatment with an IV antimicrobial agent
- *Grade >2 AST or ALT elevation: (AST or ALT >3 \times ULN) in combination with total bilirubin >2 \times ULN or clinical jaundice as defined by Hy's law*
- *Grade \geq 3 AST or ALT elevation: (AST or ALT >5 \times ULN)*
- Any Grade 3 or greater thrombocytopenia (National Cancer Institute Common Terminology Criteria for Adverse Events [NCI CTCAE v4.0]): *Platelets <50,000/mm³*
- Any Grade 4 neutropenia (NCI CTCAE v4.0): *ANC <500/mm³*

Patients who discontinue study treatment *and who do not remain in the blinded study will be* asked to return to the clinic for an early termination visit (see Section [4.6.1](#)) followed by 8 weeks of safety follow-up.

The primary reason for study treatment discontinuation should be documented on the appropriate eCRF. Patients who discontinue study treatment prematurely will not be replaced.

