5.1.3 Management of Study Treatment in Patients Who Experience Specific Adverse Events

Guidelines for management of study treatment in patients who experience specific adverse events are provided in [Table 5](#).

If there are any other situations where it seems appropriate to hold and/or discontinue study treatment, please discuss with the Medical Monitor before reinitiating treatment.

Table 5 Guidelines for Management of Study Treatment in Patients Who Experience Specific Adverse Events

Event	Action to Be Taken ^a

Infection ^b
 
Serious infection or any infection requiring treatment with an IV antimicrobial agent
 
Self-limited infections that require treatment
	
Discontinue study treatment and report event as an adverse event of special interest.
 
Withhold study treatment during antimicrobial therapy. Study treatment may resume after consultation with the Medical Monitor.

Bleeding
	
Any Grade ≥ 2 bleeding event is considered an adverse event of special interest and should be reported to the Sponsor in an expedited manner.
 
For serious (Grade ≥ 3) bleeding events, withhold study treatment and consult with the Medical Monitor.

Neutropenia ^c
 
Grade 2: ANC > 1000–1500/mm³
 
Grade 3: ANC 500–1000/mm³
 
Grade 4 ANC < 500 /mm³
	
Maintain study treatment dosing.
 
For the first event, hold study treatment and recheck CBC in 7 days. If neutrophil count has recovered to Grade 1 (> 1500/mm³) or has returned to the normal range, study treatment can be resumed. If Grade 3 neutropenia persists or for recurrent Grade 3 neutropenia, discontinue study treatment.
 
Discontinue study treatment.

Thrombocytopenia ^d
 
Grade 1: PLT > 75,000/mm³
 
Grade 2: PLT 50,000–75,000/mm³
 
Grade ≥ 3: PLT < 50,000/mm³
	
In the absence of bleeding event(s), maintain study treatment dosing.
 
For the first event, hold study treatment and recheck CBC in 7 days. If platelet count has recovered to Grade 1 or has returned to the normal range, study treatment can be resumed. For recurrent Grade 2 thrombocytopenia and in the absence of bleeding events, discuss with the Medical Monitor (or discontinue study treatment).
 
Discontinue study treatment.

Gastrointestinal effects
 
Nausea, vomiting, and/or diarrhea
	
Manage according to site institutional guidelines.
 
Consider administration of GDC-0853 with food as a possible mitigation strategy.

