Table 5 Guidelines for Management of Study Treatment in Patients Who Experience Specific Adverse Events (cont.)

Event	Action to Be Taken ^a

Malignancy
 
Any malignancy
	
Discontinue study treatment with the exception of non-serious local and resectable basal or squamous cell carcinoma of the skin. Report event as an adverse event of special interest to the Sponsor in an expedited manner.

Hepatotoxicity
 
AST or ALT > 3.0–5.0 × ULN
 
AST or ALT > 3 × ULN in combination with a total bilirubin > 2 × ULN, of which at least 35% is direct bilirubin, or clinical jaundice
 
AST or ALT > 5 × ULN
	
Withhold study treatment and consult with the Medical Monitor
 
Discontinue study treatment. Report event(s) as adverse event of special interest to the Sponsor in an expedited manner.
 
Discontinue study treatment. Any elevation of an AST or ALT > 5 × ULN should be reported as an adverse event of special interest to the Sponsor in an expedited manner.

Cardiovascular effects
 
Sustained (at least two ECG measurements > 30 minutes apart) QTcF that is > 500 ms and/or > 60 ms longer than the baseline value
 
Sustained absolute QTcF that is > 515 ms
 
An episode of torsades de pointes or a new ECG finding of clinical concern
	
Unless there is a clear alternative cause other than study drug, discontinue study treatment. ^e
 
Unless there is a clear alternative cause other than study drug, discontinue study treatment. ^e
 
Unless there is a clear alternative cause other than study drug, discontinue study treatment. ^e

Vascular inflammation
 
Vasculitis
	
Consult with the Medical Monitor.

Hypersensitivity reactions
 
Fever, chills, pruritis, urticaria, angioedema, and skin rash
 
Cardiopulmonary reactions, including chest pain, dyspnea, hypotension, or hypertension
 
Persistent gastrointestinal symptoms (e.g., crampy abdominal pain, vomiting)
	
The patient should be treated according to the standard of care for management of anaphylaxis/anaphylactoid or a hypersensitivity reaction. The patient must discontinue study treatment.

Table 5 Guidelines for Management of Study Treatment in Patients Who Experience Specific Adverse Events (cont.)

CBC=complete blood count; IV=intravenous; MTX=methotrexate; PLT=platelet count; QTcF=QT interval corrected using Fridericia's formula ; SC=subcutaneous; ULN=upper limit of normal.

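### Stopping rules disagree for vasculitis (Sections 1.3 and 5.1.1.8 against Table 5) and for skin carcinoma (Section 4.6.2 against Table 5)

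*Combined protocol and SAP*

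**What the plan says.** **Vasculitis.** Section 1.3 states: "Study drug should be discontinued in any patient who develops an adverse event of vasculitis, and the patient should enter the safety follow-up period". Section 5.1.1.8 repeats the rule almost word for word: "Study drug should be discontinued in any patient who develops an adverse event of vasculitis, and the patient should enter safety follow up". It then adds: "Guidelines for management of study treatment in the event of vasculitis in patients are provided in" Table 5. In Table 5 (Section 5.1.3), the whole entry for vasculitis is the instruction to "consult with the Medical Monitor".

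**Scope of the stop.** Sections 1.3 and 5.1.1.8 refer to study drug. Section 4.6.2 applies to both products; for the events it lists, patients must permanently "discontinue study treatment with both oral study drug and SC comparator drug". The note under Table 5 likewise defines study treatment as the oral study drug plus, in Cohort 1, the SC comparator.

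**Malignancy.** Section 4.6.2 lists malignancy among its mandatory reasons for permanent discontinuation, with no qualifier. Section 5.1.1.9 refers the reader to Table 5 for managing study treatment in this event. That row reads: "Discontinue study treatment with the exception of non-serious local and resectable basal or squamous cell carcinoma of the skin".

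**The concern.** These are safety rules that the protocol wrote for risks it names itself. For vascular inflammation, Section 5.1.1.8 reports findings in dogs in the 4-week study (at 56 µM·h and above) that had not fully reversed after recovery and had no consistent clinical biomarker. It reports none in the 9-month study up to 36 µM·h, notes that Beagles are prone to a spontaneous arteritis, and calls translatability to humans unknown. Where laboratory markers may not track an event, the written instruction for the moment of diagnosis carries more of the load.

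Table 5 is the page a site is likely to open when an event occurs. If it says less than the section text, or something different from Section 4.6.2, two sites can follow the current protocol and treat the same event differently. What is at stake is consistent patient protection across sites.

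**Working it through.** No arithmetic applies, and the plan states no figure to reproduce. The check sets the current sections side by side; the summary of changes at the front of the amendment is not used as evidence.

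| Event | Section text | Table 5 |
|---|---|---|
| Vasculitis | 1.3 and 5.1.1.8: stop study drug, go to safety follow-up | Consult the Medical Monitor; no hold or stop |
| Basal or squamous cell skin carcinoma (non-serious, local, resectable) | 4.6.2: permanent stop for any malignancy | Exempt from the stop |

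**Step 1: can the vasculitis row be read as implying a stop?** Table 5's own drafting points the other way. Where it wants an action together with consultation, it writes both. For serious bleeding the row says "withhold study treatment and consult with the Medical Monitor", and for AST or ALT above 3 and up to 5 times ULN it says "Withhold study treatment and consult with the Medical Monitor". The table has 10 event categories: infection, bleeding, neutropenia, thrombocytopenia, gastrointestinal effects, malignancy, hepatotoxicity, cardiovascular effects, vascular inflammation and hypersensitivity. Eight contain at least one instruction to hold, withhold or discontinue. The other two (10 − 8 = 2) are gastrointestinal effects and vascular inflammation. Section 5.1.1.5 orders no stop for gastrointestinal effects, so that row agrees with its section. Vascular inflammation is the only category whose section orders a stop and whose row contains no hold or stop at all.

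**Step 2: what exactly would stop?** The note under Table 5 and the legend to Figure 1 both separate study drug (GDC-0853 or its placebo) from the SC comparator. Read that way, Sections 1.3 and 5.1.1.8 stop the tablets and are silent on the injections. In Arm E the tablets are placebo and the injection is adalimumab, so the literal reading would leave the active product running. The protocol is not strict about the term, however: Section 5.3.5.1 refers to an injection of study drug. The scope cannot be settled from the text. The gap concerns Cohort 1 only, because Cohort 2 has no injections.

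**Step 3: where does the patient go after stopping?** For vasculitis only Sections 1.3 and 5.1.1.8 name a path (safety follow-up), and they agree. Footnote a of Table 5 asks patients who must stop for safety reasons specified in the table to stay in the blinded study to Week 12, if the investigator thinks it appropriate. The vasculitis row specifies no stop, so the footnote does not reach it today. If a stop were written into the row, the footnote would apply and would differ from the two sections. This is not a present conflict, but it has to be settled in the same edit.

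**Step 4: skin carcinoma.** Take a patient with a non-serious, local, resectable squamous cell carcinoma of the skin. Section 4.6.2 requires a permanent stop and Table 5 exempts the same patient. Section 4.6.2 contains no exception and no pointer to Table 5, and the protocol states no order of precedence.

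**The case against.** For vasculitis, the strongest reply is that nothing contradicts. Table 5 does not say to continue or to resume. A site can stop and then consult, and a reader who reaches Table 5 from Section 5.1.1.8 has just read the instruction to stop. Consultation also brings each case to the Medical Monitor, which limits divergence between sites. Much of this stands: a reader might infer that Table 5 permits treatment to continue after vasculitis, and the documents do not say that. What remains is that the row omits the stop its own section orders, in a table that elsewhere writes action and consultation together.

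A reader might also take the absence of vasculitis from the Section 4.6.2 list as a further conflict. It carries no weight. That list is not exhaustive: Table 5 also orders discontinuation, with its own qualifications, for sustained QTcF prolongation and for persistent or recurrent Grade 3 neutropenia, and Section 4.6.2 lists neither.

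For skin carcinoma, one can argue that Table 5 is the more specific text, is named by Section 5.1.1.9, and should govern. That is a reasonable reading, but the site has to supply it. Section 4.6.2 is worded as mandatory, and where the protocol wants a skin-carcinoma exception elsewhere, as in the eligibility criteria, it writes one. The conflict is narrow, since it concerns only minor skin cancers arising during 12 weeks of treatment, but it is literal.

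**Conclusion.** Both discrepancies are in the current text and should be fixed. For vasculitis, Table 5 leaves out a stop that Sections 1.3 and 5.1.1.8 order, and the scope of that stop in Cohort 1 is unclear. For skin carcinoma, Section 4.6.2 and Table 5 give opposite instructions for the same patient.

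The reach is limited to patients who have one of these two events. The rules apply in both cohorts, but that does not make the whole trial the number affected. A reader might infer a bias in Day 84 ACR50, through patients who leave early and are imputed as non-responders. The documents do not support that: they give no rate for either event, so no such effect can be sized and none is claimed.

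The conclusion rests only on reading the sections as written, with no precedence between them. It takes no view on which clinical rule is right.

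**What to change.** 1. **Vasculitis:** reconcile Sections 1.3 and 5.1.1.8 with the vascular inflammation row of Table 5 so that one action is stated everywhere. In the same edit, state whether the action covers the SC comparator in Cohort 1, and whether the patient goes to safety follow-up or is asked to remain to Week 12.
2. **Skin carcinoma:** reconcile the malignancy entry in Section 4.6.2 with the malignancy row of Table 5 so that both carry the same rule, with or without the exception.

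The sponsor's safety team decides the content of each rule. The cost is amendment wording and a short memo to sites, with no new procedures, visits or patients.

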5.1.1.9 Malignancy

The impact of BTK inhibition on the development of malignancies is not known; however, malignancies have been identified as a potential concern for immunomodulatory agents. Malignancies have been reported in patients with XLA, including lymphoreticular malignancies, gastric and colorectal adenocarcinoma, and squamous cell carcinoma of the lung.

Patients with a history of cancer, including hematologic malignancy and solid tumors, within 10 years before screening will be excluded from the study. Basal or squamous cell carcinoma of the skin that has been excised and is considered cured and in situ carcinoma of the cervix treated with apparent success by curative therapy more than 1 year prior to screening are not exclusionary.

All malignancies are adverse events of special interest and should be reported to the Sponsor in an expedited manner as outlined in Section 5.2.3.

Guidelines for management of study treatment in the event of malignancies in patients are provided in [Table 5](#). Please refer to the GDC-0853 Investigator's Brochure for further details.

5.1.2 Potential Risks with Adalimumab

Investigators should be aware of the risks associated with ADA and their management, including serious infections, injection-site reactions, liver enzyme elevations, headache, and rash (for full details, see the local prescribing information).

5.1.2.1 Hypersensitivity Reactions

Patients with a history of anaphylactic or other serious allergic reaction to ADA are excluded from study participation.

Investigators and HCPs administering study injections should be trained to recognize and manage the signs and symptoms of a potential anaphylactic/anaphylactoid or hypersensitivity reaction and to accurately and appropriately report these events.

HCPs should also instruct patients how to recognize the signs and symptoms of any anaphylactic/anaphylactoid or hypersensitivity reaction and to contact a health-care provider and/or seek emergency care in case of any such symptoms. See [Appendix 7](#) for clinical criteria for diagnosing anaphylaxis (Sampson's criteria).

Guidelines for management of study treatment in the event of hypersensitivity reactions in patients are provided in [Table 5](#).

